6.2 Exclusion criteria

Subjects are not permitted to enroll in the study if any of the following criteria are met:

- 1a. Subject has been previously randomized in this study (re-screening for screen-failed subjects is only allowed with prior consultation and permission of the medical monitor).
2. Subject has participated in another study of an investigational medicinal product (IMP) or a medical device during the 2 months immediately prior to Visit 1 or is currently participating in another study of an IMP or a medical device.
3. Subject has any medical or psychiatric condition that, in the opinion of the investigator, could jeopardize or would compromise the subject's ability to participate in this study.
- 4a. Subject has been previously treated with LCM and the LCM treatment was stopped due to lack of efficacy or adverse event(s).
5. Subject has a known hypersensitivity to any component of the study medication.
6. Subject has a medical condition that could be expected, in the opinion of the investigator, to interfere with study medication absorption, distribution, metabolism, or excretion.
7. Subject has experienced febrile seizures exclusively. The occurrence of febrile seizures in addition to partial-onset seizures is not exclusionary.
- 8a. Subject is on a ketogenic diet that has either changed within the 4 weeks prior to Visit 1 or is expected to change during the study.
- 9a. Subject has creatinine clearance <30mL/minute.
10. Subject has a clinically relevant ECG abnormality, in the opinion of the investigator (eg, second or third degree heart block at rest or a corrected QT interval [QTc] \geq 450ms).
11. Subject has a hemodynamically significant congenital heart disease.
12. Subject has an arrhythmic heart condition requiring medical therapy.
13. Subject has a known history of severe anaphylactic reaction secondary to medication intake or serious blood dyscrasias.
14. Subject has nonepileptic events that could be confused with seizures. Subjects may be included if epileptic events can be clearly distinguished and the frequency meets the study inclusion criteria.
- 15a. Subject has a current diagnosis of Lennox-Gastaut syndrome, epilepsy partialis continua, primary generalized epilepsy, Dravet Syndrome, or seizures that are not of partial-onset origin.
- 16a. Subject has a history of generalized convulsive status epilepticus \leq 2 months prior to Screening (Visit 1).
19. Subject has been treated with felbamate and has experienced any serious toxicity issues (defined as liver failure, aplastic anemia) with this treatment. Subjects treated with felbamate for <12 months are excluded. Subjects treated with felbamate for \geq 12 months prior to Visit 1 and who have not experienced serious toxicity issues are eligible.
20. Subject has an acute or subacutely progressive central nervous system disease. Subject has epilepsy secondary to a progressing cerebral disease or any other progressively neurodegenerative disease (malignant brain tumor or Rasmussen Syndrome).

- 21a. Subject has a known cardiac sodium channelopathy, such as Brugada syndrome.
22. Subject has >2x upper limit of normal (ULN) of any of the following: alanine aminotransferase (ALT), aspartate aminotransferase (AST), alkaline phosphatase (ALP), or >ULN total bilirubin ($\geq 1.5 \times \text{ULN}$ total bilirubin if known Gilbert's syndrome). If subject has elevations only in total bilirubin that are >ULN and <1.5xULN, fractionate bilirubin to identify possible undiagnosed Gilbert's syndrome (ie, direct bilirubin <35%).

For randomized subjects with a Baseline result >ULN for ALT, AST, ALP, or total bilirubin, a Baseline diagnosis and/or the cause of any clinically meaningful elevation must be understood and recorded in the electronic Case Report form (eCRF).

If subject has >ULN ALT, AST, or ALP that does not meet the exclusion limit at screening, repeat the tests, if possible, prior to dosing to ensure there is no further ongoing clinically relevant increase. In case of a clinically relevant increase, inclusion of the subject must be discussed with the Medical Monitor.

Tests that result in ALT, AST, or ALP up to 25% above the exclusion limit may be repeated once for confirmation.

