3 STUDY OBJECTIVE(S)

The primary objective of this study is to evaluate the efficacy of LCM administered concomitantly with 1 to 3 AEDs in subjects ≥ 1 month to <4 years of age with epilepsy who currently have uncontrolled partial-onset seizures.

The secondary objective is to evaluate the safety and tolerability of LCM in subjects ≥ 1 month to <4 years of age with epilepsy who currently have uncontrolled partial-onset seizures.

An additional objective is to evaluate the PK of LCM in children ≥ 1 month to <4 years of age.

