5.4 Rationale for study design and selection of dose

Epilepsy is a condition for which an improved benefit/risk ratio for medicinal products remains a challenge; this is especially true for pediatric patients. Based on the demonstrated efficacy and safety of LCM as adjunctive treatment in subjects aged ≥ 16 years of age, and the experience with other AEDs in pediatric subjects, it is likely that LCM will be an efficacious and safe treatment in the pediatric population with uncontrolled partial-onset seizures.

SP0967 is a Phase 3, multicenter, double-blind, randomized, PBO-controlled, parallel-group study to evaluate the efficacy and safety of LCM as adjunctive therapy in subjects ≥ 1 month to < 4 years of age with epilepsy who have uncontrolled partial-onset seizures.

Based on the currently available LCM pediatric PK, safety, and tolerability data from SP847 and SP1047, as well as on information available in the medical literature, the recommendations for SP0967 are as follows:

- Subjects must weigh ≥ 4 kg to < 30 kg at Visit 1.
- Feeding tube administration is permitted for subjects who are unable to swallow the oral solution.
- Titration should occur over a 20-day period; with LCM dose increased by 2mg/kg/day every 4 days until the target dose (LCM 8mg/kg/day to 12mg/kg/day, or matching PBO) is achieved. All subjects will start on a dose of LCM 4mg/kg/day or matching PBO at the start of the Titration Period.
- During the Titration Period, step-back titration by LCM 1mg/kg/day or LCM 2mg/kg/day will be permitted to allow subjects with reduced tolerability to remain in the study depending on tolerability (ie, based on investigator judgment and legal representative[s]/caregiver[s] feedback). If study medication is back titrated, the dose must never be lower than LCM 4mg/kg/day (or matching PBO) and must be maintained for ≥ 3 days (in order to reach steady state) before subsequent titration to a higher dose.
- During the Titration Period, subjects may also have the dose of study medication held steady or titrated to a higher dose. If study medication is titrated to a higher dose, the subject must remain on that dose for ≥ 4 days unless a step-back titration based on tolerability is required.
- The LCM dose should remain fixed over the Maintenance Period.

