6 SELECTION AND WITHDRAWAL OF SUBJECTS

6.1 Inclusion criteria

To be eligible to participate in this study, all of the following criteria must be met:

1. An Institutional Review Board (IRB)/Independent Ethics Committee (IEC) approved written Informed Consent form is signed and dated by the parent(s) or legal representative(s)/caregiver(s) (in accordance with local regulation).
2. Subject's parent(s) or legal representative(s)/caregiver(s) is considered reliable and capable of adhering to the protocol visit schedule or medication intake according to the judgment of the investigator.
3. Subject is male or female from ≥ 1 month (ie, 4 weeks after full term [37 weeks gestational age]) to < 4 years of age. For preterm infants < 1 year old, the corrected gestational age should be used when determining eligibility. The generally accepted definition of corrected gestational age, which is calculated by subtracting the number of weeks born before 37 weeks of gestation from the chronological age, will be used for this study.
4. Subject has a diagnosis of epilepsy with partial-onset seizures. The results of ≥ 1 prior EEG and ≥ 1 magnetic resonance imaging/computerized tomography scan should be consistent with this diagnosis.
5. Subject weighs ≥ 4 kg to < 30 kg at Visit 1.
7. Subject has experienced ≥ 2 partial-onset seizures with or without secondary generalization during each consecutive 7-day period during the 2 weeks prior to Visit 1.
- 8a. Subject has ≥ 2 partial-onset seizures with or without secondary generalization during the End-of-Baseline video-EEG. Electrographic seizures are defined as recognizable ictal patterns on an EEG involving ≥ 2 contiguous electrodes. The seizures are initiated as a unilateral or strongly asymmetric abnormal epileptiform discharge lasting a total of > 10 seconds.
9. Subject is on a stable (concurrently or sequentially) dosage regimen of 1 to 3 AEDs. The dosage regimen of concomitant AED therapy must be kept constant for a period of ≥ 2 weeks prior to Visit 1. A stable daily dosage regimen of a concomitant benzodiazepine (BZD) will be considered as a concomitant AED.
10. Vagus nerve stimulation is allowed and will not be counted as a concomitant AED. The VNS device must have been implanted for ≥ 6 months prior to Visit 1; device settings must be kept stable for ≥ 2 weeks prior to Visit 1 and kept stable during the Baseline, Treatment, and Transition Periods. Use of the VNS device magnet is allowed.

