7.2 Treatment(s) to be administered

At Visit 3, subjects will be randomized in a double-blind manner to 1 of 2 parallel treatment arms: LCM or PBO in a 1:1 ratio. Randomization will occur after completion of the End-of-Baseline video-EEG and after confirmation that the subject has met selection criteria. Randomization will be stratified by age category (≥ 1 month to < 6 months of age, ≥ 6 months to < 1 year of age, ≥ 1 year to < 2 years of age, and ≥ 2 years to < 4 years of age).

At the end of Visit 3, subjects should take the first dose of study medication while in the clinic. At each subsequent clinic visit, subjects should take study medication (and any concomitant AEDs) at the regular time(s). Study medication will be administered orally bid (at approximately 12-hour intervals in the morning and in the evening).

SP0967 will target Maintenance Period doses of LCM 8mg/kg/day to 12mg/kg/day or matching PBO.

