7.2.3 Transition Period

During the Transition Period, subjects randomized to PBO will be transitioned in a double-blind manner from PBO to LCM 8mg/kg/day over a 12-day period. Transition dosing will be administered according to Table 7-2. Subjects randomized to LCM will remain on their Maintenance Period dose during the Transition Period.

Table 7-2: Transition Period LCM dosing schedule for subjects randomized to PBO

Maintenance Period	LCM doses for the Transition Period		
	Day 28 to Day 31	Day 32 to Day 35	Day 36 to 39
PBO	4mg/kg/day	6mg/kg/day	8mg/kg/day

LCM=lacosamide; PBO=placebo

At Visit 1 of EP0034, all subjects will transition to a dose of LCM 10mg/kg/day. The SP0967 final Transition Visit is the same as Visit 1 of EP0034.

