7.8 Concomitant medications/treatments

7.8.1 Permitted and prohibited concomitant treatments (medications and therapies)

Subjects must have been maintained on a stable dosage regimen of 1 to 3 marketed AEDs for ≥ 2 weeks prior to Visit 1.

Vagus nerve stimulation is allowed and will not be counted as concomitant AED use. The VNS device must have been implanted for ≥ 6 months prior to Visit 1, kept at a stable setting for ≥ 2 weeks prior to Visit 1, and kept stable during the Baseline, Treatment, and Transition Periods. Use of the VNS device magnet is allowed.

For subjects who enter the Taper Period, AEDs may be added or adjusted and VNS adjustments may be made at the discretion of the investigator.

The following concomitant medications are prohibited during the study:

- Clozapine
- Monoamine oxidase-A inhibitors
- Barbiturates (except as AEDs)
- Cannabidiols (not approved or indicated for epilepsy by local health authority)

Neuroleptics (except for clozapine) are allowed during the study but the investigator should make every effort to keep the dose stable.

Subjects who have been treated with felbamate and have experienced any serious toxicity issues are excluded from the study. Any subject who is currently treated with felbamate, and has received felbamate for a period of less than 12 months, is excluded from the study. Subjects treated with felbamate for ≥ 12 months prior to Visit 1 and who have not experienced serious toxicity issues are eligible.

The following medications are not allowed unless used as described:

- Amphetamines: stable use only.

A stable daily dosage regimen of concomitant BZDs will be considered as a concomitant AED. Such use is permitted throughout the study and should be maintained for the video-EEG procedures. Use of BZDs as rescue medications (ie, not as part of a stable daily dosing regimen) is permitted. However, use of BZDs for any reason other than a stable daily dosage regimen as concomitant AED within 24 hours prior to or during the video-EEG is not permitted and may lead to the subject being withdrawn from the study (**May** Withdrawal Criterion 5; Section 6.3).

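### The eligibility rules as written do not bar a child already taking prescribed lacosamide, whose total dose could then exceed 12 mg/kg/day; probably very rare and cheap to close

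*Protocol*

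**What the plan says.** **Who may enter.** Exclusion 4a (Protocol 6.2) applies where "Subject has been previously treated with LCM and the LCM treatment was stopped due to lack of efficacy or adverse event(s"). Exclusion 2 removes children in another investigational study, now or within the previous 2 months, so it reaches LCM supplied by a trial but not LCM on prescription. Inclusion 9 (Protocol 6.1) asks that "Subject is on a stable (concurrently or sequentially) dosage regimen of 1 to 3 AEDs". Protocol 7.8.1 repeats this as a "stable dosage regimen of 1 to 3 marketed AEDs". Neither makes an exception for LCM, which Protocol 2 describes as approved from 4 years of age.

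**What may be taken.** In 7.8.1 the list under "The following concomitant medications are prohibited during the study" has four entries: clozapine, monoamine oxidase-A inhibitors, barbiturates other than as antiepileptic drugs (AEDs), and cannabidiols not approved or indicated for epilepsy. LCM is not among them. The SAP contains no bar either.

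**What dose is given.** Under Protocol 5.4, "All subjects will start on a dose of LCM 4mg/kg/day or matching PBO at the start of the Titration Period". Under 7.2, "SP0967 will target Maintenance Period doses of LCM 8mg/kg/day to 12mg/kg/day or matching PBO". In the Transition Period (7.2.3), "subjects randomized to PBO will be transitioned in a double-blind manner from PBO to LCM 8mg/kg/day". Tables 7-1, 7-2 and 7-3 count study drug only, and nothing tells the site to subtract LCM from another source.

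**Intent.** The primary objective (Protocol 3) is to "evaluate the efficacy of LCM administered concomitantly with 1 to 3 AEDs", which treats LCM as separate from the background drugs.

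**The concern.** Taken literally, the criteria admit a child on a stable prescribed dose of LCM, counted as one of the 1 to 3 background AEDs. That child could then be randomized to more LCM on top.

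What is at stake is the dose given to an individual infant or toddler. The trial's top dose is 12 mg/kg/day, which is also the highest dose that Protocol 2 describes for SP847, SP848 and EP0034. Protocol 11.3 lists arrhythmias, including atrioventricular block and marked bradycardia, and syncope among the adverse events of special interest for LCM. Protocol 2 reports a dose relationship for common adverse events in adults. The site would be blinded to whether study LCM was being added.

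Efficacy is a lesser matter. If LCM already present reduces the further effect of study LCM, the treatment difference shrinks slightly.

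**Working it through.** **1. Does any rule exclude the child?** Take a child under 4 on stable prescribed LCM who still has seizures.

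| Rule | Result for this child |
|---|---|
| Exclusion 4a | Not met: LCM has not been stopped |
| Exclusion 2 | Not met: LCM is prescribed, not trial supply |
| Inclusion 9 and 7.8.1, background AEDs | Met: LCM is a marketed AED and is not excepted |
| 7.8.1 prohibited list | LCM not listed |
| Table 5-1, footnote e | Use is recorded at Visit 1, with no rule attached |
| 8.1.1, Visit 1 procedures | No LCM plasma sample |

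The child passes.

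**2. The plan's own dose ceiling.** The start is 4 mg/kg/day with four steps of 2: 4 + 4×2 = 12 mg/kg/day, which agrees with Table 7-1.

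**3. Total dose with background b.** The documents give no value of b, so 2, 4 and 6 mg/kg/day are assumptions.

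- Active arm, Maintenance: b+8 to b+12.
- Placebo arm, Transition (Table 7-2): b+4, b+6, b+8.
- The active-arm total exceeds 12 when b > 12 − study dose: any b>0 at study dose 12, b>2 at 10, and b>4 at 8.

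| Assumed b | Active arm, Maintenance | Placebo arm, Transition steps |
|---|---|---|
| 2 | 10 to 14 | 6, 8, 10 |
| 4 | 12 to 16 | 8, 10, 12 |
| 6 | 14 to 18 | 10, 12, 14 |

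**4. The plan's own power.** Inputs are from Protocol 13.6. For change in average daily frequency (ADF): difference 0.249, SD 0.62, 99 per arm, two-sided 5%. A two-sample t calculation (noncentral t) gives 80.3%, against 80% stated. For responders at 20% v 40% with 99 per arm, the continuity-corrected test gives 83.6%, against approximately 83% stated.

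**5. Effect on power.** Let c be the share of such children and f the fraction of the effect that they keep. The ADF difference becomes 0.249×(1 − c(1−f)), and the active responder rate becomes 0.40 − 0.20×c(1−f). The documents give neither c nor f. Shares of 1% and 2% are assumed, which is 198×0.01 ≈ 2 and 198×0.02 ≈ 4 evaluable children.

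| c | f | ADF difference | Power, ADF | Active responder rate | Power, responders |
|---|---|---|---|---|---|
| 0 | any | 0.2490 | 80.3% | 40.0% | 83.6% |
| 1% | 0 (worst) | 0.2465 | 79.5% | 39.8% | 82.9% |
| 2% | 0 (worst) | 0.2440 | 78.7% | 39.6% | 82.1% |
| 1% | 0.5 | 0.2478 | 79.9% | 39.9% | 83.3% |
| 2% | 0.5 | 0.2465 | 79.5% | 39.8% | 82.9% |

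The largest losses are 80.3 − 78.7 = 1.6 points and 83.6 − 82.1 = 1.5 points.

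**The case against.** The case against giving this weight is strong.

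- **Intent is clear.** The objective, the common starting dose and the placebo-to-LCM transition all treat LCM as the added drug. A site that stacked it would depart from the evident meaning, and Protocol 11.1.7 requires dosing beyond the protocol to be recorded. This stands as evidence of an omission, but none of it excludes a child.
- **No such child is shown to exist.** Every participant is under 4 and approval starts at 4. SP1047 did dose children with LCM that they had been prescribed, but Protocol 2 does not say that any of them was under 4. This stands.
- **Several safeguards would have to fail.** Visit 1 reveals the use. Titration allows holds and back-titration (7.2.1). Second- or third-degree atrioventricular block, a confirmed QTc of 500 ms or more, or the investigator's judgment leads to withdrawal (6.3). These reduce the risk, but apart from the Visit 1 record and the investigator's judgment they act only after exposure.

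Two stronger readings are tempting, and the documents support neither. A reader might infer that the protocol means to allow or invite stacking; the objective and dosing sections point the other way. A reader might also infer that a placebo child on background LCM contaminates the control arm. Both primary variables compare the End-of-Maintenance video-EEG with the End-of-Baseline video-EEG (Protocol 4.1.1), and stable background LCM is present at both, so it does not alter change on placebo. Any dilution comes only from a smaller added effect in the active arm.

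**Conclusion.** The gap is real and lies in the current text: a stated eligibility rule, followed as written, can lead to a dose above the trial's maximum. It appears to be a drafting omission. The dose arithmetic is certain once b is given, but b and the number of such children are unknown, and approval only from 4 years makes them probably very rare. The loss of power is under 2 points even with a 2% share and no added effect, and the sample size needs no change. The reason to act is the safety of an occasional child, not the validity of the trial. The priority is low.

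**What to change.** Add *or is currently receiving LCM* to exclusion 4a. List non-study LCM as prohibited in Protocol 7.8.1 until the last dose of study medication, including the Taper Period.

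The end point matters. Protocol 5.1 and 7.8.1 let AEDs be added once taper begins, but Table 7-3 still gives 9 mg/kg/day in the first taper step after 11 or 12. With an assumed b of 4, lifting the prohibition at the start of taper would allow 4 + 9 = 13 mg/kg/day.

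Stating in inclusion 9 that LCM cannot be a background AED is optional. Any interval since last LCM use is for the sponsor's clinical team to set.

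With these changes b = 0 and total LCM is at most 12 mg/kg/day. The analyses do not change. The cost is amendment wording with the approvals required by Protocol 14.5, across about 140 planned sites, and the loss of at most a few candidates. SAP 4.6 (May 2020) already plans an analysis of the first 244 enrolled, which suggests recruitment near or beyond plan, although the documents do not give its status. If few children remain to be enrolled, a written clarification to sites would bring most of the benefit. The SAP 6.4.4 table of AEDs on the day of first dose, by drug name, would show whether any such child was enrolled.

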6.3 Withdrawal criteria

Parent(s)/legal representative(s) are free to withdraw the subject from the study at any time, without prejudice to their continued care. The following criteria for subject withdrawal from SP0967 are outlined below. Additional discontinuation criteria for potential drug-induced liver injury (PDILI) are presented in Section 6.3.1.

Subjects **must** be withdrawn from the study if any of the following events occur:

1. Subject experiences intolerable AEs, including clinically relevant abnormal laboratory findings that, in the opinion of the investigator, preclude further participation in the study.

Subjects who are unable to tolerate study medication will be withdrawn from the study as follows:

- Subjects unable to achieve or maintain target dose for the final 3 days of the Titration Period
2. The sponsor or a regulatory agency requests withdrawal of the subject.
 3. Subject has QTc interval of ≥ 500 ms that is confirmed by a cardiologist over-read on any ECG.
 4. Subject develops a second or third degree atrioventricular (AV) block.
 5. Subject is unwilling or unable to continue, or the parent(s)/legal representative(s)/caregiver(s) is unwilling or unable to allow the subject to continue in the study.
 6. Investigator's decision that withdrawal from further participation would be in the subject's best interest.
 7. Subject experiences generalized convulsive status epilepticus.

Subjects **may** be withdrawn from the study if any of the following events occur:

1. Subject has any clinically relevant change in medical or psychiatric condition and in the opinion of the investigator, the condition warrants discontinuation from the study.
2. Subject requires a medication that is not permitted by the protocol.
3. Subject's legal representative(s)/caregiver(s) (in accordance with local regulation) is noncompliant with study procedures or medication, in the opinion of the investigator.
5. Subject uses BZDs within 24 hours prior to or during video-EEG for any reason other than a stable daily dosage regimen as a concomitant AED. The Medical Monitor should be contacted if withdrawal is being considered. Use of a stable daily dosage regimen of a concomitant BZD (ie, 1 of the Baseline concomitant AED[s]) should be maintained for the video-EEG procedures.

Investigators should attempt to obtain information for subjects who withdraw. For subjects considered as lost to follow up, the investigator should make an effort (at least 1 phone call and 1 written message to the parent[s] or legal representative[s]/caregiver[s]), and document his/her effort (date and summary of the phone call and copy of the written message in the source documents), to complete the final evaluation. All results of these evaluations and observations, together with a narrative description of the reason(s) for removing the subject, must be recorded in the source documents. The eCRF must document the primary reason for withdrawal.

Investigators should contact the Medical Monitor, whenever possible, to discuss the withdrawal of a subject in advance.

Subjects withdrawn from the study will proceed to the blinded Taper Period described in Section 7.2.4 and the assessments described in Table 5-3 will be performed.

Subjects who are withdrawn from the study will not be replaced.

